1.2 Secondary Aims

1.2.1 To compare progression-free survival and overall survival between patients receiving dinutuximab, irinotecan and temozolomide with and without the addition of DFMO.

1.2.2 To define the toxicity profile of DFMO administered with dinutuximab, irinotecan and temozolomide.

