			TEM0 mg	IRIN mg	DIN mg	GM-CSF mcg			
Enter calculated dose above and actual dose administered below									
		1	mg	mg					a-o
		2	mg	mg	mg				d, o
		3	mg	mg	mg				d, o
		4	mg	mg	mg				d, o
		5	mg	mg	mg				d, o
		6					mcg	n	
		7					mcg		
		8					mcg	c, d, e	
		9					mcg		
		10					mcg		
		11					mcg		
		12					mcg		
		15						c, d, e	
		21							
		22	Begin Cycle 2 on Day 22 or when peripheral counts recover with ANC $\geq 750/\mu\text{L}$ and platelets $\geq 75,000/\mu\text{L}$ (whichever occurs later).						

See [Section 5.0](#) for Dose Modifications for Toxicities and the COG Member website for Supportive Care Guidelines.

4.4.2 Required Observations in Regimen A Cycle 1

Page 2 of 2

All baseline studies must be performed prior to starting protocol therapy unless otherwise indicated below.

- a. History, physical exam with vital signs, performance status*
- b. Height, weight, BSA*
- c. CBC with differential and platelets (patients who experience Grade 4 neutropenia should have CBCs checked at least twice per week until recovery to Grade 3)*
- d. Electrolytes, BUN, creatinine, calcium, magnesium, phosphorus, albumin*
- e. ALT, total bilirubin*
- f. Pregnancy test (obtain for females of childbearing potential)
- g. ECHO or MUGA
- h. Audiogram or BAER – May be obtained within 3 weeks prior to the start of protocol therapy.
- i. Bilateral bone marrow aspirates and biopsies
- j. Cross sectional tumor imaging of original primary site and any non-osseous sites of disease involvement at study entry (MRI or CT) (submit for central review as soon as scan is obtained; see [Section 15.1](#) for imaging details for patients without measurable disease)
- k. ¹²³I-MIBG scan (submit for central review as soon as scan is obtained)
- l. Curie score profile (patients with MIBG avid disease; see [Appendix IX](#) for worksheet) (submit for central review as soon as scan is obtained)
- m. FDG-PET scan for patients with ¹²³I-MIBG non-avid disease (submit for central review as soon as scan is obtained)
- n. Specimens for correlative studies. Post-dinutuximab specimens should be collected at a single time point between Day 6 and Day 9. See [Section 14](#) and [Appendix X](#) for details.
- o. Faces Pain Scale Revised – can be done anytime on Day 1 of therapy. On Days 2-5 of therapy, should be performed at least 4 hours after the dinutuximab infusion has begun. See [Section 14.1.3](#) for additional detail.

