4.7.2 Required Observations in Regimen B Cycle 2 and Subsequent Cycles

- a. History, physical exam with vital signs, performance status
- b. Height, weight, BSA
- c. CBC with differential and platelets (patients who experience Grade 4 neutropenia should have CBCs checked at least twice per week until recovery to Grade 3). If patients remain on study for > 4 cycles and cytopenias are not observed, CBCs should be obtained at the start of subsequent cycles and as clinically indicated
- d. Electrolytes, BUN, creatinine, magnesium, phosphorus, albumin
- e. ALT, total bilirubin
- f. Audiogram or BAER (use same mode of testing as baseline). Obtain at the end of Cycle 2 and end of every 2nd cycle thereafter.
- g. Bilateral bone marrow aspirates and biopsies. Obtain at the end of Cycles 2, 4, 6, and every fourth cycle[&] thereafter for patients with bone marrow involvement at baseline (study enrollment) or patients with *any* prior history of bone marrow involvement. Obtain at the end of Cycles 2 and 6 for all patients, including those without bone marrow involvement at baseline (study enrollment) and those without *any* prior history of bone marrow involvement.*
- h. Cross sectional tumor imaging of original primary site and any non-osseous sites of disease involvement at study entry (MRI or CT) (submit for central review as soon as scan is obtained after Cycles 2, 4, and 6). Obtain at the end of Cycles 2, 4, 6, and every fourth cycle[&] thereafter. Patients with no measurable or non-measurable soft tissue disease (i.e., MIBG avid bone lesions or bone marrow involvement only) at baseline are only required to obtain appropriate cross-sectional imaging (CT and/or MRI) at baseline and at the end of Cycles 2 and 6 (see [Section 15.1](#) for imaging details).*
- i. ¹²³I-MIBG scan (submit for central review as soon as scan is obtained after Cycles 2, 4, and 6). Obtain at the end of Cycles 2, 4, 6, and every fourth cycle[&] thereafter.*
- j. Curie score profile (patients with MIBG avid disease; see [Appendix IX](#) for worksheet) (submit for central review as soon as scan is obtained after Cycles 2, 4, and 6). Obtain at the end of Cycles 2, 4, 6, and every fourth cycle[&] thereafter.
- k. FDG-PET scan for patients with ¹²³I-MIBG non-avid disease (submit for central review as soon as scan is obtained after Cycles 2, 4, and 6). Obtain at the end of Cycles 2, 4, 6, and every fourth cycle[&] thereafter.*

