- l. Specimens for correlative studies (see [Section 14](#) and [Appendix X](#) for specimen requirements). On Day 1 of Cycle 2, specimens should be collected prior to initiation of therapy.
- m. Faces Pain Scale Revised – can be done anytime on Day 1 of therapy. On Days 2-5 of therapy, should be performed at least 4 hours after the dinutuximab infusion has begun. Obtain for Cycles 2, 4, 6, and 12. See [Section 14.1.3](#) for additional detail.

*Imaging and bilateral bone marrow aspirates and biopsies may be performed within 1 week prior to the start of the next planned cycle of therapy.

[&] Patients enrolled on study prior to Amendment 4 only.

This listing only includes evaluations necessary to address the primary and secondary aims. OBTAIN OTHER STUDIES AS REQUIRED FOR GOOD CLINICAL CARE.

Comments

(Include any held doses, or dose modifications)

4.7.3 Treatment Details for Regimen B Cycle 2 and Subsequent Cycles (3 weeks = 1 cycle)

Drug doses should be calculated based on the BSA using height and weight obtained within 1 week prior to the beginning of each cycle.

Suggested administration schedule for eflornithine, chemotherapy and dinutuximab (Days 2-5):

- At hour 0: patient should receive oral eflornithine (DFMO) and oral temozolomide. Medications should be given separately, not mixed.
- At hour 1: patient should start IV irinotecan over 90 minutes, and on days patient is receiving dinutuximab infusion (Days 2-5 of each cycle), start IVF bolus of normal saline (10-20 mL/kg) over 1 hour.
- At hour 2.5: on days patient is receiving dinutuximab infusion (Days 2-5 of each cycle), start dinutuximab infusion.

Eflornithine (DFMO): PO daily (NG or Gtube administration is allowed)

Days: 1 – 7 and 15 - 21

Dose: 2250 mg/m²/dose TID (6750 mg/m²/day). See dosing table in [Appendix XII](#)

Note: During Days 1-5, consider giving one of the 3 times daily eflornithine doses and temozolomide close together in order to minimize potential for emesis and redosing.

The eflornithine dose should be rounded to the nearest 500 mg (0.5 g). Please see [Appendix XIII](#) for eflornithine administration recommendations. Please provide these instructions to patient families.

If emesis occurs within 20 minutes of taking a dose of eflornithine, then the dose should be repeated once. If emesis occurs after 20 min, the dose should not be repeated.

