It is not known if dinutuximab is excreted in breast milk. IgG molecules are excreted in breast milk. Due to the potential for serious adverse reactions in the nursing infant, breastfeeding is not recommended.

Toxicity:**Comprehensive Adverse Events and Potential Risks list (CAEPR)
for
Dinutuximab (MoAb 14.18, chimeric, NSCs 623408 and 764038)**

The Comprehensive Adverse Events and Potential Risks list (CAEPR) provides a single list of reported and/or potential adverse events (AE) associated with an agent using a uniform presentation of events by body system. *Frequency is provided based on 359 patients.* Below is the CAEPR for dinutuximab (MoAb 14.18, chimeric).

Version 2.9, January 10, 2019⁶⁰

Adverse Events with Possible Relationship to dinutuximab (CTCAE 5.0 Term) [n= 359]		
Likely (>20%)	Less Likely (<=20%)	Rare but Serious (<3%)
BLOOD AND LYMPHATIC SYSTEM DISORDERS		
	Anemia	
	Disseminated intravascular coagulation	
		Hemolytic uremic syndrome ⁶¹
CARDIAC DISORDERS		
		Cardiac arrest
		Sinus bradycardia
	Sinus tachycardia	
EYE DISORDERS		
		Eye disorders - Other (eye disorders) ⁶²
GASTROINTESTINAL DISORDERS		
	Abdominal pain	
	Diarrhea	
	Nausea	
	Vomiting	
GENERAL DISORDERS AND ADMINISTRATION SITE CONDITIONS		
	Edema limbs	
Fever		
	Generalized edema	
Pain		
		Sudden death NOS
IMMUNE SYSTEM DISORDERS		
	Allergic reaction	
		Anaphylaxis
	Serum sickness	

Adverse Events with Possible Relationship to dinutuximab (CTCAE 5.0 Term) [n= 359]		
Likely (>20%)	Less Likely (<=20%)	Rare but Serious (<3%)
INFECTIONS AND INFESTATIONS		
	Infection ⁶³	
		Myelitis ⁶⁴
INJURY, POISONING AND PROCEDURAL COMPLICATIONS		
		Infusion related reaction
INVESTIGATIONS		
	Alanine aminotransferase increased	
	Aspartate aminotransferase increased	
	Creatinine increased	
Investigations - Other (elevated c-reactive proteins)		
	Lymphocyte count decreased	
	Neutrophil count decreased	
	Platelet count decreased	
	White blood cell decreased	
METABOLISM AND NUTRITION DISORDERS		
	Anorexia	
	Hyperkalemia	
	Hypoalbuminemia	
	Hypocalcemia	
	Hypokalemia	
	Hyponatremia	
MUSCULOSKELETAL AND CONNECTIVE TISSUE DISORDERS		
	Back pain	
	Pain in extremity	
NERVOUS SYSTEM DISORDERS		
	Neuralgia	
		Peripheral motor neuropathy
	Peripheral sensory neuropathy ⁶⁵	
		Reversible posterior leukoencephalopathy syndrome
RENAL AND URINARY DISORDERS		
	Proteinuria	
		Renal and urinary disorders - Other (atonic urinary bladder) ⁶
	Urinary retention ⁶⁵	
RESPIRATORY, THORACIC AND MEDIASTINAL DISORDERS		

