7.1 End of Therapy & Follow-up

See COG Late Effects Guidelines for recommended post treatment follow-up:

<http://www.survivorshipguidelines.org/>

Note: Follow-up data are expected to be submitted per the Case Report Forms (CRFs) schedule.

STUDIES TO BE OBTAINED	End of Therapy	Disease Progression	Follow up			
			Year 1 30 days	Year 1 6 months*	Year 1 12 months*	Years 2 -5 Annually*
History	X					
Physical Exam with VS	X					
Ht, Wt, BSA	X					
Performance Status	X					
CBC, differential, platelets	X					
Electrolytes, BUN, Creatinine	X					
ALT, total bilirubin, albumin	X					
CT/MRI ¹	X ²	X				
MIBG (or FDG-PET if ¹²³ I-MIBG non-avid disease)	X ²	X				
Bilateral bone marrow aspirates and biopsies	X ²	X				
Audiogram	X		X ³		X	
Disease status	X		X	X	X	X
Toxicity/Significant events	X		X	X	X	X
Survival/Vital status	X		X	X	X	X

* +/- 2 months

1. Cross-sectional imaging should be of the original primary site and any non-osseous disease sites present at study enrollment or at time of progression.

2. For patients who experienced their first response (MR, PR, CR) at the time of the end therapy evaluation, a complete confirmatory disease evaluation should be performed *at least* 4 weeks after the end of therapy evaluation.

3. If the patient underwent an audiogram within 28 days prior to end of therapy (ie, at the end of the previous cycle), the end of therapy audiogram should be done 30 days +/- 7 days from the end of therapy date.

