9.3.4 Assessment of Study Objectives

The primary study aim ([1.1.1](#)) will be assessed by a one-sided continuity-corrected test of proportions with pooled variance to compare the response rates after 6 cycles in the two regimens, and the futility and efficacy monitoring rules ([Section 9.3.3](#)). The response rate by the end of 6 cycles will be calculated on each regimen, including placement of a 95% confidence interval. If a patient is a responder and later has PD or goes off protocol therapy, then the patient will be counted as a responder. If the response rate on Regimen B is significantly better, then it will be considered a therapeutic regimen worthy of further testing in patients with newly-diagnosed high-risk neuroblastoma. In addition, the response rate by the end of 6 cycles (based on confirmed responses) will also be calculated for each regimen, with responders defined as patients who achieve a confirmed minor response or better per the revised INRC⁶⁸ as their best overall response by the end of 6 cycles as determined by central review.

To address secondary objective [1.2.1](#), Kaplan-Meier curves of PFS and OS will be generated by regimen and compared using log-rank tests. PFS and OS will also be evaluated separately in the cohorts of patients enrolled prior to and post-Amendment 4 given the reduction in maximum cycles of therapy from 17 to 6 cycles.

To assess secondary aim [1.2.2](#), toxicities (Grade ≥ 3) experienced on Regimen B will be descriptively summarized.

Exploratory aim [1.3.1](#) will be assessed by exploring the relationship between response (responder vs. non-responder) after 6 cycles on Regimen B with serum cytokine levels (IL1, IL6, TNF-alpha, IFN-gamma, etc.), tumor resident immune cells (NK cells, TAMS, TILS), and critical immune cell suppressing proteins (B7H3, PDL-1) using Fisher's exact test for categorical and Wilcoxon rank-sum test for continuous factors.

To address exploratory objective [1.3.2](#), GD2 levels in tumor cells from bone marrow samples will be correlated with response (responder vs. non-responder) after 6 cycles using Fisher's exact test for categorical and the Wilcoxon rank-sum test for continuous factors.

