11.12 Routine Adverse Event Reporting

Note: The guidelines below are for routine reporting of study specific adverse events on the COG case report forms and do not affect the requirements for CTEP-AERS reporting.

Routine reporting is accomplished via the Adverse Event (AE) Case Report Form (CRF) within the study database. For this study, routine reporting will include all toxicities reported via CTEP-AERS and all Grade 3 and higher Adverse Events.

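### Calcium is missing from the Regimen B chemistry list from Cycle 2 onward (4.7.2, item d), so hypocalcemia may be under-detected on the experimental arm

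*Combined protocol and SAP*

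**What the plan says.** Each regimen has two required-observations lists, one for Cycle 1 and one for Cycle 2 onward. Item d is the chemistry panel in all four.

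- In 4.4.2 (Regimen A, Cycle 1), 4.5.2 (Regimen A, Cycle 2 onward) and 4.6.2 (Regimen B, Cycle 1), item d reads "Electrolytes, BUN, creatinine, calcium, magnesium, phosphorus, albumin".
- In 4.7.2 (Regimen B, Cycle 2 onward), item d reads "Electrolytes, BUN, creatinine, magnesium, phosphorus, albumin".

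The closing note of 4.7.2 explains the status of the list: "This listing only includes evaluations necessary to address the primary and secondary aims". It then leaves any other tests to good clinical care. The end-of-therapy table in 7.1 has a row for "Electrolytes, BUN, Creatinine" and a separate row for ALT, bilirubin and albumin, with no calcium in either.

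Three other places bear on the point. The dinutuximab adverse event list in 6.2 includes "Hypocalcemia" in its column for frequencies of 20% or less. Secondary aim 1.2.2 is "To define the toxicity profile of DFMO administered with dinutuximab, irinotecan and temozolomide"; for that aim, 9.3.4 says that Grade 3 or higher toxicities "experienced on Regimen B will be descriptively summarized". Routine reporting under 11.12 covers "all toxicities reported via CTEP-AERS and all Grade 3 and higher Adverse Events".

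**The concern.** Calcium is absent from one of four otherwise matching lists, and that list governs the experimental arm for every cycle after the first. No section explains why the test would be needed on Regimen A but not on Regimen B from Cycle 2. Dinutuximab, the agent that carries the hypocalcemia risk in the documents, is given on Days 2-5 of every cycle on both regimens.

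A laboratory abnormality without symptoms is found only if someone measures it. If sites follow 4.7.2 literally, such events on Regimen B after Cycle 1 could go unrecorded. The toxicity summary for aim 1.2.2 would then be incomplete for this term, on the arm it is meant to describe. Any informal comparison of hypocalcemia between the arms would also rest on unequal testing and lean toward fewer detected events on Regimen B.

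**Working it through.** The plan states no figure to reproduce. The check compares the four lists, looks for another calcium requirement, and counts scheduled tests from the therapy delivery maps.

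**1. Could electrolytes be meant to include calcium?** The other three lists name both, so the protocol treats them as separate. A site reading 4.7.2 literally is not told to measure calcium.

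**2. Does another section restore it?** The end-of-therapy table in 7.1 has no calcium. Section 5 has no dose or management rule that uses calcium. The last scheduled item d on Regimen B that contains calcium is therefore Cycle 1 Day 15 (delivery map, 4.6.1).

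**3. Days carrying item d, from the delivery maps**

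| Period | Days with item d | Draws | Calcium included? |
|---|---|---|---|
| Regimen A, Cycle 1 (4.4.1) | 1-5, 8, 15 | 5 + 1 + 1 = 7 | Yes |
| Regimen B, Cycle 1 (4.6.1) | -6, 1-5, 8, 15 | 1 + 5 + 1 + 1 = 8 | Yes |
| Regimen A, each later cycle (4.5.1) | 1-5 | 5 | Yes |
| Regimen B, each later cycle (4.7.1) | 1-5 | 5 | No |

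**4. Scheduled calcium tests for a patient who completes all cycles**

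Total = Cycle 1 tests + (number of cycles - 1) x calcium tests per later cycle. Section 4.1 sets the maximum at 6 cycles for patients enrolled on Amendment 4 or later, and at 17 for those enrolled before it.

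| | Regimen A | Regimen B as written | Regimen B with calcium added |
|---|---|---|---|
| 6 cycles | 7 + 5 x 5 = 32 | 8 + 5 x 0 = 8 | 8 + 5 x 5 = 33 |
| 17 cycles | 7 + 16 x 5 = 87 | 8 + 16 x 0 = 8 | 8 + 16 x 5 = 88 |

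The gap after Cycle 1 is 5 x 5 = 25 tests over 6 cycles, or 16 x 5 = 80 over 17. With the correction, Regimen B has one more test than Regimen A, which is the Day -6 draw of the DFMO lead-in.

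**5. From tests to events.** The documents give only a band of 20% or less for hypocalcemia. They give no rate for Grade 3 or higher and no information on how often sites test calcium unprompted. The number of missed events cannot be calculated.

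**The case against.** The case on the other side accepts the omission and disputes its weight.

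- **Clinical practice fills much of the gap.** Chemistry is still drawn on Days 1-5, sites are told to add tests for good care, and any Grade 3 or higher value they find is reportable under 11.12. A patient who enters with hypocalcemia must have it reassessed under 11.5.1. This stands: the loss is mainly confined to events without symptoms that only a scheduled draw would catch, and how many are lost depends on site practice, which the documents do not describe.
- **No between-arm test of hypocalcemia is planned.** Section 9.3.4 only describes toxicity on Regimen B, and the one numerical between-arm toxicity rule (9.5) concerns hearing loss. This stands as far as formal analysis goes. However, 2.5 commits the trial to watching for more toxicity on the DFMO arm than on the standard arm, even though it singles out diarrhea and hearing loss. The Regimen B summary is affected whether or not the arms are compared.
- **The documents tie hypocalcemia to dinutuximab, not to DFMO.** True. But aim 1.2.2 concerns DFMO given with dinutuximab, irinotecan and temozolomide, so events of the combination belong in the summary.
- **The counts are maxima.** They assume that every cycle is completed, and many patients will stop earlier. The 17-cycle figure also assumes that the present wording applied throughout to patients enrolled before Amendment 4. In addition, 4.4.2 and 4.6.2 require the baseline chemistry to be repeated if it is more than 72 hours old, which can add one test in Cycle 1 on either arm. These caveats stand, but they do not alter the contrast of 5 against 0 per cycle from Cycle 2.

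**Conclusion.** The concern holds as an internal inconsistency with a minor consequence. As written, 4.7.2 schedules no calcium test on Regimen B after Cycle 1 Day 15, while 4.5.2 schedules five per cycle on Regimen A. At full treatment this is 8 tests against 32 over 6 cycles, or 8 against 87 over 17. These are counts of scheduled tests, not of missed events.

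The missing word is certain. Under-detection is possible but unquantified, and it rests on the assumption that at least some sites follow the list literally. At stake is the completeness of one laboratory term in the summary for aim 1.2.2. The response endpoint, power, type I error and dose modification rules are not affected.

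**What to change.** Insert calcium in item d of 4.7.2 so that it matches 4.5.2 and 4.6.2. Both regimens would then have five scheduled calcium tests per cycle from Cycle 2.

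The cost is one word at the next amendment and one more analyte on a panel already drawn on Days 1-5 of each cycle. No extra visit or blood draw day is needed.

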4.7.5 Additional guidance

- Capillary leak syndrome is an expected side effect of dinutuximab therapy. Complications of capillary leak syndrome can be mitigated if euolemia is maintained. Close monitoring of heart rate and urine output is required, and fluids should be adjusted to compensate for third space losses. The routine use of diuretics during Days 2-5 is contraindicated unless clinically required (i.e. pulmonary capillary leak with respiratory compromise). Use of furosemide should be avoided when feasible due to ototoxicity concerns.
- Corticosteroid therapy should be used only for life-threatening conditions (i.e. treatment of increased intracranial pressure in patients with CNS tumors, symptomatic bronchospasm, stridor unresponsive to other measures or life-threatening allergic reactions). Corticosteroids will impair the immune activation that is a critical part of the protocol therapy. **The use of steroids at any time during immunotherapy requires clear justification and documentation.**
- The use of IVIG is discouraged. IVIG should not be given within 2 weeks of starting dinutuximab treatment and 1 week after completing dinutuximab therapy.
- Cytokines or growth factors (G-CSF, Interferon, etc.) not included in the Treatment Plan are prohibited during immunotherapy.

5.0 DOSE MODIFICATIONS FOR TOXICITIES

In addition to dose modifications, this section provides information regarding management of toxicities known to be associated with protocol therapy.

In the sections below, when protocol therapy is to be discontinued, all protocol therapy should be discontinued. If treating clinicians elect to continue to administer dinutuximab, irinotecan and temozolomide, this can be done as part of clinical care but will not be considered protocol therapy.

NOTE: If eflornithine is stopped for any reason (e.g. toxicity or, for patients enrolled prior to Amendment 4, tumor resection after Cycle 6 disease evaluation) and then resumed at same or lower dose, at least 5 days of the resumed/decreased dose of eflornithine should be given prior to starting Day 1 of the next cycle of chemotherapy. The resumed/decreased dose should be given for a total of 12 days. Please HOLD eflornithine for 24 hours prior to tumor resection.

If a subsequent cycle is delayed by \leq 7 days for any event that is unlikely related to eflornithine (e.g. timing adjustments, count recovery, or toxicity not attributed to eflornithine), the patient should continue eflornithine until the next cycle begins. If a subsequent cycle is delayed $>$ 7 days for any event that is unlikely related to eflornithine, the patient should stop taking eflornithine until he/she meets eligibility to start the subsequent cycle. Once the patient is eligible to start the next cycle, 5 days of eflornithine (Day -4 to Day 0) should be given prior to starting Day 1 of the next cycle of chemoimmunotherapy.

